**Study Outcomes**

**Primary Outcome**

1. Change in insulin sensitivity index based on the effect of insulin on glucose metabolism in the FSIVGTT.

**Secondary Outcomes**

1. Change in fasting plasma glucose and insulin levels.
2. Change in area under the curve (AUC) insulin, AUCglucose/AUCinsulin, and insulin sensitivity index based on OGTT.
3. Change in pre- and post-prandial glucose levels.
4. Change in basal triglyceride level.
5. Change in free fatty clearance based on the effect of insulin on FFA in the FSIVGTT.
6. Change in HDL, LDL, and total cholesterol levels.
4. Change in weight, BMI, neck, waist and hip circumference. It is unlikely that these parameters will change with the short duration of administration, however.
5. Change in blood pressure. It is unlikely that these parameters will change with the short duration of administration, however.
6. Whole-body rate of regenerating cortisol (measured with 9,11,12,12-[(2)H(4)]cortisol tracer) will be analyzed in collaboration with [name]. On metabolism by dehydrogenation, d4F loses 11alpha- deuterium, forming trideuterated cortisone (d3E) and is regenerated by reduction to tri-deuterated cortisol (d3F). 11BHSD1 reductase activity can be measured specifically as conversion of d3E to d3F (40). The amount of regenerated cortisol at baseline will be assessed for correlation with basal measures of insulin sensitivity and triglyceride levels, and the change in these parameters in response to mifepristone.
7. Adverse events will be tallied and compared between treatments.

8. Change in total and free testosterone, androstenedione, DHEAS, ACTH and cortisol will be assessed between treatments as a measure of mifepristone effect.
9. Change in 5 alpha and beta-reduced cortisol metabolites, cortisol, cortisone and their tetra-hydro metabolites will be assessed between treatments.
10. Correlation between post-treatment mifepristone level and the change in triglyceride levels and insulin sensitivity in response to mifepristone.

## STUDY ANALYSIS

The study will be analyzed in collaboration with [name], Ph.D. (Biostatistics and Clinical Epidemiology Service, Clinical Center). Subjects will be randomized in blocks of 6 into the two treatment arms. Means and standard deviations will be used to describe continuous data. Proportions and frequencies will be used to describe categorical data. All continuous data will be examined for normality and homogeneity of variances, and will be either transformed as appropriate or assessed using non-parametric tests. The change in continuous variables (including triglyceride, HDL, LDL and total cholesterol levels, insulin sensitivity index, pre- and post-prandial glucose values, whole body cortisol production rates, blood pressure, weight, and waist circumference) before and after study intervention will be analyzed using paired t-tests or Wilcoxon signed-rank test. Correlation of continuous data (e.g., regenerated cortisol and insulin sensitivity and triglyceride levels, and mifepristone level and insulin sensitivity and triglyceride response) will be carried out by Pearson's correlation coefficient or Spearman's rho, as appropriate. Between and within treatment comparisons will be done using Mixed Models for a crossover design that will also consider sequence effect, if any. Difference in the proportion of subjects who meet criteria for metabolic syndrome, or other categorical data, before and after study intervention will be analyzed using McNemar's test. Two-sided p-values will be used for all analysis and the level of statistical significance will be set a priori at 0.05. The stepdown Bonferroni correction will be used to adjust for multiple comparisons. All statistical analysis will be performed using SAS v. 9.2 (SAS Institute, Cary, NC).

Human data on the effect of mifepristone on insulin sensitivity index are lacking. This will therefore be a pilot study of 17 subjects. Data from this study will then be used to design a long-term study looking at the effect of mifepristone on glucose intolerance, lipids, weight and blood pressure. With an estimated loss-to-follow-up rate of 15%, we would need to recruit a total of 25 patients. Thus, we plan to screen approximately 80 patients to account for the high ineligibility rate and patient drop-outs prior to study initiation.

Based on current evidence, a compensatory rise in ACTH levels has been seen with mifepristone in healthy individuals at doses as low as 100 mg/day (when used as a single dose over 3 months) and 200 mg/day over 8 days (41 - 42). Given the uncertainty in the effect of the dose, we plan to do an interim analysis looking at the effect of the proposed dose (50 mg every 6 hours) on the HPA axis in the first 6 subjects (one randomization block). The data from the first 6 subjects will be unblinded to [name], the study statistician, only. If the 24 hour UFC value post mifepristone treatment is more than or equal to twice the upper limit of normal in four or more of the six subjects, then we will decrease the mifepristone dose to 25 mg every 6 hours (100 mg/day). However, if there is no significant increase in the levels (< twice the upper limit of normal), same dose of mifepristone will be continued throughout the study. If the mifepristone

dose is changed based on the results of the interim analysis, then the data from the first six subjects will not be used in the final analysis and 15 additional subjects will be enrolled prior to completion of the study. On the other hand, if no dose adjustment is required, the study analysis will be done as previously planned.

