### *Study for eligible subjects*

This crossover study has two treatment arms (placebo or Mifepristone 50 mg tablets every six hours) with each subject serving as her own control. After eligibility is confirmed, subjects will undergo baseline testing and will be randomized to one of the treatment arms. Testing will be performed before and at the end of seven days of treatment with the study agent. Study drug will be continued until completion of post-drug testing. Thus, subjects will take the study drug for a total of nine days during each treatment arm. There will be a washout period of at least six and no more than eight weeks after which subjects will be randomized to the other arm of the study with an identical testing schedule. Subjects will record any symptoms or adverse events on a calendar

throughout the study. Women will be asked to keep a record of any abnormal menstrual bleeding. Subjects will be asked not to start on any new diet or exercise regimen during the study and maintain a stable weight for at least 2 weeks prior to study entry.

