**Figure 1: Study Design overview**

*Procedures during each treatment*

Subjects will be admitted to the 5SWN metabolic unit or 5NW in the Clinical Center on a Sunday for testing the following day. To accommodate menstrual cycle timing, and for subjects for whom weekend testing is preferable, admission may occur on Friday or Saturday; additionally the Day 2 and 3 testing may be swapped if needed to accommodate nursing scheduling. To reduce potential variability associated with estrogen in premenopausal women, testing will be performed in the early follicular phase (days 1-7 of menstrual cycle). In case of perimenopausal women with irregular menstrual cycles, an attempt will be made to begin testing in the early follicular phase with the rest of the testing performed at pre-determined study intervals. Height, weight, and waist, hip and neck circumference (mean of three measurements) will be measured. Waist circumference will be measured at the intersection of midaxillary line with the uppermost lateral border of the right iliac crest at the end of a normal expiration (36). The hip circumference will be measured in a horizontal plane at the level of the maximal circumference of hips and buttocks. Neck circumference will be measured at mid-neck height between the mid-cervical spine and mid anterior neck to within 1 mm (37). Weight will be measured at the same time of the day on the same scale. All measurements will be taken after an overnight fast with the subject standing upright, both arms hanging loosely by the side of body, and eyes directed straight ahead. Subjects will be maintained on an isocaloric regular diet during the inpatient part of the study. Those subjects who are on metformin at the time of study entry will be maintained on the same dose of metformin throughout the study.

Day 1 (Monday)

- Fasting blood pressure will be measured consecutively three times five minutes apart. Blood pressure will be measured in a standardized manner in the morning using equipment that meets certification criteria. Measurements will begin after at least 5 minutes of rest in a supine position. Subjects will be asked to refrain from smoking or ingesting caffeine during the 30 minutes preceding the blood pressure measurement. Blood pressure will be measured in the same arm on

each occasion using an appropriate cuff size with the bladder in the cuff encircling at least 80 percent of the arm for accurate measurement.

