#### Day 10 – 12 (Wednesday-Friday):

After an overnight fast, all study procedures indicated for day 1 -3 will be repeated on day 10 - 12. Blood (5 ml) will be obtained on day 10 for measurement of post-treatment mifepristone level and to hold for other potential measurements related to cortisol metabolism. Subjects will continue on the study drug until the completion of all study procedures on day 12.

Day 19 and 33 (Friday): Safety monitoring

After discontinuation of study drug, subjects will return approximately one week (Day 19) and then 3 weeks (Day 33) after the last day of study drug intake for measurement of blood chemistries and CBC. The research team will make every effort to ensure that these safety follow-up visits are within 2 days of day 19 and day 33. However, for subject convenience, we will allow for the follow-up visits to be within 5 days of the expected date of follow-up (day 19 ± 5 days and day 33 ± 5 days). In these cases, a member of the study team will contact the study subject on the expected date of follow-up to ensure that the subject is doing well. If any potential treatment-related abnormalities/adverse events are noted at the safety visits, subjects will receive appropriate treatment for these abnormalities and will be followed closely as clinically indicated until the abnormalities/adverse events have fully resolved.

Second study treatment visit: These study procedures will be repeated with each study drug after a wash-out period of 6-8 weeks.

For subject convenience, we will allow for the pre-study drug testing (Days 1 through 3) in each treatment arm to be done on days other than as specified above as long as it is done no more than 10 days prior to study drug initiation.

Table 1: Schema for first admission testing. The second admission will be identical.

Sunday	Monday	Tuesday	Wednesday	Thursday	Friday	Saturday
Admit to 5SWN or 5NW	DAY 1 Fasting labs 24 hr urine  0900 Serial 24 h ACTH/Cortisol  Pre & post prandial glucose levels	DAY 2 0900 Complete serial ACTH/Cortisol  0930 Fasting lipids FSIVGTT  Can go out on pass	DAY 3 0800 3 hr OGTT  1800 START MIFEPRISTONE OR PLACEBO	DAY 4 On pass	DAY 5 On pass	DAY 6 On pass

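### The primary variable is assigned to a before-after paired test and, by general wording, to a crossover mixed model, and the plan does not say which contrast decides the primary hypothesis

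*Combined protocol and SAP*

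**What the plan says.** - **Primary Outcome:** "Change in insulin sensitivity index based on the effect of insulin on glucose metabolism in the FSIVGTT". No comparator is named.
- **Study Hypothesis:** glucose abnormalities are expected to improve on mifepristone. Placebo is not mentioned.
- **Study Analysis, first method:** the insulin sensitivity index is named in a list of variables whose change "before and after study intervention will be analyzed using paired t-tests or Wilcoxon signed-rank test".
- **Study Analysis, second method:** "Between and within treatment comparisons will be done using Mixed Models for a crossover design that will also consider sequence effect, if any". No outcomes are listed, and period is not mentioned.
- **Study Analysis, non-normal data:** continuous data "will be either transformed as appropriate or assessed using non-parametric tests".
- **Study Analysis, error control:** two-sided tests at 0.05, with a stepdown Bonferroni correction whose family of comparisons is not defined.
- **Secondary Outcomes:** an explicit comparison between treatments is written for the items on adverse events, on hormones and on cortisol metabolites. The primary outcome has no such wording.
- **Size:** "This will therefore be a pilot study of 17 subjects". The Precis gives 15.

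**The concern.** The trial is a randomized, placebo-controlled crossover, yet the only test that names the primary variable is the before-after one. Three readings are open:

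1. A within-arm test of the change on mifepristone. It does not use placebo.
2. A paired test of the mifepristone-period change against the placebo-period change. It keeps placebo but ignores period.
3. The between-treatment contrast from the crossover mixed model.

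Readings 1 and 3 answer different questions and can give different answers on the same data. If the choice is made after the data are seen, the 0.05 level has no fixed meaning. A within-arm test also credits mifepristone with any change that would have occurred on placebo. The results are meant to design a longer trial, so the choice of estimate carries forward even though this is a pilot.

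**Working it through.** The plan gives no effect size, SD or power for the primary variable, so there is no figure of its own to reproduce on this point.

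**Inputs from the documents:** n=17 (Study Analysis) or 15 (Precis); two-sided alpha 0.05; two periods; stepdown Bonferroni.

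**Assumed:** normally distributed changes with SD 1 in each period; correlation ρ between a subject's two changes of 0, 0.3 or 0.5; sequences of 9 and 8 subjects (8 and 7 at n=15).

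**The two tests**
- Within-arm: t = mean(D_M) / (s/√n), where D_M is the change on mifepristone; df = n−1 = 16; critical t 2.120.
- Placebo contrast: take each subject's period 1 minus period 2 change. The treatment estimate is half the difference between the two sequence means, with standard error ½·s_p·√(1/9 + 1/8); df = n−2 = 15; critical t 2.131.

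Both use the mifepristone change. The correlation between D_M and the mifepristone-minus-placebo difference is (1−ρ)/√(2(1−ρ)) = √((1−ρ)/2), which is 0.71, 0.59 and 0.50 for ρ = 0, 0.3 and 0.5. The tests are related but far from interchangeable.

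**Step 1. No drug effect, no shift (simulation).** Each test alone rejects in 5%. Two independent tests would give 1 − 0.95² = 9.75% for at least one; the correlation lowers this somewhat. Under stepdown Bonferroni on this pair, the first rejection needs the smaller p-value to be at most 0.05/2 = 0.025.

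| ρ | At least one significant, each at 0.05 | Same, with stepdown Bonferroni on the pair |
|---|---|---|
| 0 | 8.5% | 4.4% |
| 0.3 | 8.9% | 4.6% |
| 0.5 | 9.2% | 4.7% |

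n=15 and n=17 agree within about 0.1 percentage point.

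**Step 2. Assumed drug effect of 0.5 SD, no shift, n=17 (simulation).** The within-arm test is significant in about 49%. The placebo contrast is significant in about 27-28%, 37% and 49% for ρ = 0, 0.3 and 0.5. Exactly one of the two is significant in 31%, 32% and 35% of trials.

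**Step 3. Shift common to both periods, no drug effect.** The within-arm test follows a noncentral t with noncentrality d√n. For an assumed shift d = 0.25 SD in all subjects at n=17, this is 0.25 × √17 = 1.03, and the test rejects in 16%. The shift cancels from the placebo contrast, which stays at 5%.

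**Step 4. Reading 2, with a signed-rank test.** Pairing the two periods' changes at n=17 gives null rejection of 4.6%, 3.4% and 1.6% for an assumed period effect of 0, 0.5 and 1.0 SD. It is conservative, not inflated, because unmodelled period differences add to the spread.

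**Step 5. Rank alternative.** A rank-sum test comparing within-subject period differences between the two sequences holds its size at about 4.5-4.9%, and a constant period shift does not affect it.

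**The case against.** **The design implies the answer.** In a placebo-controlled crossover the mifepristone-placebo contrast is the natural primary comparison, and a crossover model is planned. This stands in part: a reader might infer that the plan omits a placebo comparison, and that would be wrong. But the mixed-model sentence covers within-treatment comparisons as well, names no outcome and is not labelled primary.

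**Multiplicity is addressed.** A reader might infer from Step 1 that the false-positive rate is simply about 9%. The documents do not support that without a condition. If the stepdown Bonferroni correction covers these two tests, the rate is below 5%. Because the family is undefined, neither figure can be taken as the plan's own.

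**The shift is hypothetical.** This largely stands. The same formula gives 49% and 83% for common shifts of 0.5 and 0.75 SD, and a reader might take these as expected error rates. They need a trial-wide drift for which the documents show no source. The plan also limits several candidates: isocaloric inpatient diet, constant metformin dose, stable weight before entry, and "Subjects will be asked not to start on any new diet or exercise regimen during the study".

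**Cycle timing.** A reader might also infer a documented shift from menstrual timing. Premenopausal women are to be tested on cycle days 1-7, but the two FSIVGTTs in a period are 9 days apart (Day 2 to Day 11), or 8 if the pre-test moves to Day 3, so both cannot fall in that window. Pre-drug testing may also be earlier, "as long as it is done no more than 10 days prior to study drug initiation". This is a separate scheduling matter: the protocol gives no direction of change in insulin sensitivity and no premenopausal share.

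**Non-normal data.** The signed-rank test is not forced. Transformation is already allowed and would keep the mixed-model contrast.

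**It is a pilot.** This lowers the stakes. It does not remove the point, because the plan sets a primary hypothesis, a prespecified significance level and a multiplicity rule.

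**Conclusion.** The point holds as a gap in specification that should be fixed. The one test named for the primary variable most naturally discards placebo, and no section says which contrast is decisive.

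- **Disagreement:** about 31-35% of trials at n=17, assuming an effect of 0.5 SD of the change and ρ from 0 to 0.5. Part of this simply reflects two imperfectly correlated tests with moderate power.
- **False positives without drift:** about 8.5-9.2% if each test is run at 0.05 and either may count; about 4.4-4.7% if the stepdown correction covers the pair.
- **False positives with a common shift:** 16% for the within-arm test against 5% for the placebo contrast, at an assumed 0.25 SD in all subjects. The correction does not remove this bias. The example shows a vulnerability of the within-arm test; it is not a forecast for this trial.

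All of these rest on normal changes with equal SD in the two periods. If the paired test means pairing the two periods' changes, there is no inflation, only a conservative test that ignores period.

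**What to change.** Add to Study Analysis a statement such as: *The single primary analysis is the mifepristone-minus-placebo contrast of the change in FSIVGTT insulin sensitivity index from the crossover mixed model with treatment, period and sequence terms, at two-sided alpha 0.05.*

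Then:
- If normality fails, transform and keep this contrast. Otherwise, replace the signed-rank test with a rank-sum test comparing within-subject period 1 minus period 2 differences between the two sequences.
- Label within-arm before-after tests descriptive.

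The cost is wording only. All the data needed are already planned to be collected, with no added visits, tests or subjects.

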**Precis**

The hormone cortisol is a key regulator of metabolism that influences the use of glucose (sugar) and fat as fuels. Persistently increased cortisol levels, as in Cushing's syndrome, lead to obesity, type 2 diabetes mellitus and lipid abnormalities including elevated triglyceride levels and low high-density lipoprotein (HDL) levels. These same disorders are also present in patients without Cushing's syndrome, suggesting that cortisol may be involved in their pathogenesis. Mifepristone is a cortisol-like drug that blocks cortisol action in the body. It can reverse lipid abnormalities, diabetes and obesity in Cushing's syndrome patients but its effects on these conditions have not been tested in patients without the syndrome.

The long-term aim of this clinical trial is to evaluate the ability of mifepristone to reverse or improve glucose intolerance, dyslipidemia, hypertension and weight gain. An initial 7-day

prospective, randomized, placebo-controlled, crossover study is proposed here to look at the effect of short-term administration of oral mifepristone or placebo on glucose intolerance. Given that there are no human data available on the effect of mifepristone on insulin sensitivity, this will be a pilot study of 15 subjects. Data from this study will then be used to design a larger trial to evaluate long-term effects on blood pressure and weight, as well as glucose and triglyceride control.

Overweight or obese subjects with abnormal glucose tolerance will undergo each of the two treatments in a randomized order, including mifepristone by mouth and a look-alike inert tablet by mouth. Each treatment study will include two or three days of baseline tests that will be repeated after seven days of treatment. Treatments will be separated by at least six and no more than eight weeks. The tests will include blood drawing, urine collection, administration of glucose and insulin by vein, and a cortisol-like material to evaluate the metabolism of cortisol and a related hormone, corticosterone.

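### The pilot size is given as 15 in one place and 17 in another, and the 25 recruits attributed to 15% loss follow from neither

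*Combined protocol and SAP*

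**What the plan says.** Three parts of the combined protocol and SAP give figures for the size of the study.

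- **Precis:** "this will be a pilot study of 15 subjects".
- **Study Analysis, sample-size paragraph:** "This will therefore be a pilot study of 17 subjects", followed by "With an estimated loss-to-follow-up rate of 15%, we would need to recruit a total of 25 patients". About 80 people are to be screened "to account for the high ineligibility rate and patient drop-outs prior to study initiation".
- **Study Analysis, interim analysis paragraph:** the effect on the HPA axis is examined in the first six subjects. If the dose is changed as a result, "the data from the first six subjects will not be used in the final analysis". For enrolment in that case, the rule is: "15 additional subjects will be enrolled prior to completion of the study". Otherwise, "if no dose adjustment is required, the study analysis will be done as previously planned".

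The Precis and Study Analysis give the same reason for running a pilot: there are no human data on this drug and insulin sensitivity. Neither says whether its figure counts subjects enrolled or subjects completing. No effect size, standard deviation, power or precision target is given.

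**The concern.** The 15 and the 17 describe the same pilot, and both stand in current text. The recruitment total is worded as the consequence of a 15% loss, so it should be reproducible from one of them. It is not.

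The pilot's stated purpose is to supply data for designing a longer trial, and the number analysed determines how precise those data are. As the text stands, a reader cannot tell which target is meant or where 25 comes from. If the dose changes, a reader also cannot tell how many subjects are to be enrolled in all. The 15 in the dose-change rule matches the Precis but not the 17 given just before it in Study Analysis, and nothing is said about loss among those 15.

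**Working it through.** **Inputs.** Target 15 (Precis) or 17 (Study Analysis); loss 15% and recruitment total 25 (Study Analysis); six interim subjects, then 15 additional subjects if the dose changes (interim paragraph). The 15% is taken as one overall rate.

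**Step 1: try to reproduce 25.** Recruits needed = completers / (1 − loss).

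- From 17: 17/0.85 = 20.0, so 20.
- From 15: 15/0.85 = 17.65, so 18.
- Multiplying by 1.15 instead gives 19.55 and 17.25, which also round up to 20 and 18.

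Neither target gives 25.

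**Step 2: work backwards from 25.**

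- Completers at 15% loss: 25 × 0.85 = 21.25, about 21.
- Loss implied if 17 of 25 complete: 1 − 17/25 = 32%.
- Loss implied if 15 of 25 complete: 1 − 15/25 = 40%.

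**Step 3: look for an unstated base.** Adding the six interim subjects, who may be excluded:

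- (15 + 6)/0.85 = 24.7, so 25.
- (17 + 6)/0.85 = 27.06, so 28.
- Without inflating the six: 6 + 18 = 24, or 6 + 20 = 26.

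Only the first gives 25, and it uses 15 rather than the 17 that stands in the same paragraph as the 25.

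**Step 4: the dose-change case.** The interim paragraph does not say what the 15 subjects are additional to, or whether they are enrolled subjects or completers.

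| Reading | Total enrolled | Completers after excluding six, at 15% loss |
|---|---|---|
| 15 enrolled, additional to the six only | 6 + 15 = 21 | 15 × 0.85 = 12.75, about 13 |
| 15 completers, additional to the six | 6 + 18 = 24 | 15 |
| Recruitment continues to 25 | 25 | (25 − 6) × 0.85 = 16.15, about 16 |
| 15 additional to the planned 25 | 25 + 15 = 40 | (40 − 6) × 0.85 = 28.9, about 29 |

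**Step 5: what cutting the total would do.** If the dose changed and recruitment stopped at 20, (20 − 6) × 0.85 = 11.9 would complete. If it stopped at 18, (18 − 6) × 0.85 = 10.2 would. Both totals are also below the 21 that the interim paragraph needs at a minimum.

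**The case against.** **The 25 may be right, with only its derivation missing.** If it was set as (15 + 6)/0.85, it already contains an allowance for the six interim subjects and for loss among the 15 who follow. This is the best defence, and it means that 25 cannot be called too many. It does not clear the text. No section states this route, and it makes the 17 wrong.

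**Drop-out before the study starts might account for the excess.** It does not, because Study Analysis assigns that loss to the screening figure of about 80.

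**The 15% might apply to each of the two treatment periods.** Then 17/0.85² = 23.5, so 24, and 25 recruits would leave 25 × 0.85² = 18.1, about 18. The gap narrows, but 25 is still not reproduced from 17, and the documents do not describe a per-period rate.

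**A reader might infer that the trial is sure to be short of subjects, or underpowered.** The documents support neither. If the dose is unchanged, 25 recruits exceed what either target needs. If it changes, the figure of about 13 depends on one reading of the interim paragraph: 15 enrolled, additional to the six only. That reading is natural, but it is not the only one. The 13 also counts subjects completing both periods; the plan says "Between and within treatment comparisons will be done using Mixed Models for a crossover design", and such models can use subjects with one period. No power is claimed, so none is lost.

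**The consequence is small.** That stands, and it limits the weight of the point. It does not remove the contradiction.

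**Conclusion.** The figures conflict as written: 15 against 17, and a recruitment total of 25 where 15% loss gives 18 or 20. The excess over the stated inputs is five recruits from a target of 17, or seven from 15, taking 15% as the overall loss.

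That 25 comes from (15 + 6)/0.85 is a plausible inference and no more. If it is correct, 17 is the figure out of line, since the same route from 17 gives 28.

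There is no shortfall if the dose is unchanged. If the dose changes, a shortfall to about 13 completers is possible but not certain. No stated power or precision figure is affected, because the plan states none. This is a correction that should be made to the sample-size text, not a threat to the design.

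**What to change.** 1. State one target number of completers, the same in the Precis and in Study Analysis.
2. Restate the basis of the recruitment total so that it follows from that target, the 15% loss and any allowance for the six interim subjects. If the intent was 25 = (15 + 6)/0.85, say so and show it.
3. Do not simply replace 25 by 18 or 20. The interim paragraph needs at least 21 enrolled if the dose changes. If the dose did not change, the cut would also lower expected completers from about 21 to about 15 or 17.
4. In the interim paragraph, make the 15 consistent with the chosen target. Say whether it counts enrolled subjects or completers, and whether it falls within the 25.

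**Cost.** If the target is 15 and the basis of 25 is as inferred, this is wording only, with no extra enrolment. The downside is that a stated figure may look slightly less favourable. Only if the sponsor keeps 17 and also allows for excluding the six would the total rise, to 26 or 28 depending on whether the six are inflated for loss.

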## **STUDY HYPOTHESIS**

The primary study hypothesis is that glucose abnormalities in overweight and obese individuals will improve with short-term administration of the glucocorticoid antagonist mifepristone.

A secondary study hypothesis is that activation of the HPA axis will be minimal when mifepristone is administered in four divided daily doses of 50 mg.

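### If the interim rule changes the dose, the final analysis holds no data at 50 mg four times daily and cannot address the secondary HPA hypothesis, which is specific to that regimen

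*Combined protocol and SAP*

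**What the plan says.** STUDY HYPOTHESIS gives a secondary hypothesis tied to one regimen: "activation of the HPA axis will be minimal when mifepristone is administered in four divided daily doses of 50 mg". Under Secondary Outcomes, the matching measures are changes in ACTH and cortisol, and in cortisol, cortisone and their metabolites, compared between treatments (the items numbered 8 and 9).

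STUDY ANALYSIS sets an interim look at the first six subjects, a single randomization block. The dose is lowered if post-mifepristone 24-hour UFC is "more than or equal to twice the upper limit of normal in four or more of the six subjects". In that event, "then the data from the first six subjects will not be used in the final analysis and 15 additional subjects will be enrolled". Otherwise, "if no dose adjustment is required, the study analysis will be done as previously planned", so the six stay in.

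The exclusion is worded for the final analysis as a whole. I found nothing in the document that exempts HPA outcomes, provides a separate report of the six, or says how a dose change bears on the hypothesis.

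**The concern.** Excluding the six is reasonable for insulin sensitivity and the other metabolic outcomes, because after a dose change they received a different treatment from everyone else. For the HPA hypothesis the position is reversed: they are the only subjects treated at the dose it names. Whether they are kept depends on an HPA measurement, and the branch that removes them is the one with the strongest interim evidence against the hypothesis.

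The trigger cannot be dismissed as remote. STUDY ANALYSIS cites compensatory ACTH rises at 100 mg/day and at 200 mg/day over 8 days, and this trial gives 4 × 50 = 200 mg/day for nine days. BACKGROUND presents split dosing as a way to limit the effect on ACTH, so this hypothesis tests the reason for the regimen. The pilot is also meant to inform the design of the long-term study, which would need to know how the axis responded at 50 mg.

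**Working it through.** **The two branches side by side**

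- *Trigger met.* All later subjects receive the lower dose and the first six leave the final analysis. Subjects at 50 mg four times daily in that analysis: 6 − 6 = 0. The hypothesis as worded has no data.
- *Trigger not met.* The six are pooled with later subjects at the same dose, having been kept on condition that few exceeded the UFC limit.

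**Illustrative size**

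The plan gives no operating characteristics for the interim rule, so there is no figure of its own to reproduce. Inputs from STUDY ANALYSIS: 6 interim subjects, trigger at 4 or more, pilot size 17. Assumed: p, the true share of subjects at or above the UFC limit on 50 mg (no value is given, so it is varied); independent subjects; six evaluable at the interim; 17 completers. I read three or fewer as continue, although the continue condition mentions levels below the limit without a count.

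With X ~ Binomial(6, p):

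- chance the six are dropped = P(X ≥ 4)
- mean share in the six when kept = E[X | X ≤ 3] / 6
- mean pooled share when kept = (E[X | X ≤ 3] + 11p) / 17

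Worked at p = 0.5: P(X ≥ 4) = 22/64 = 0.344. E[X | X ≤ 3] = (6 + 30 + 60)/42 = 2.286, and 2.286/6 = 0.381. Pooled: (2.286 + 5.5)/17 = 0.458, which is 4.2 points below 0.5.

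| p | Six dropped | Share in six, if kept | Pooled share of 17, if kept | Bias (points) |
|---|---|---|---|---|
| 0.2 | 0.017 | 0.192 | 0.197 | −0.3 |
| 0.3 | 0.070 | 0.270 | 0.289 | −1.1 |
| 0.5 | 0.344 | 0.381 | 0.458 | −4.2 |
| 0.7 | 0.744 | 0.446 | 0.611 | −8.9 |

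With the Precis figure of 15 subjects, the divisor is 15 and the later subjects number 9. The bias is then −1.2 at p = 0.3 and −4.8 at p = 0.5. At p = 0.7 it is (2.679 + 6.3)/15 = 0.599, or −10.1.

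**Closer to the planned analysis**

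The share over the limit is not a planned endpoint, so a continuous between-treatment difference in log2 UFC was also simulated (17 subjects, placebo centred at half the upper limit, total SD 0.5 or 0.8, correlation 0.5 between treatments; all assumed). At a true difference of 2.0, the mean among trials that kept the dose was 1.983 (SD 0.5) or 1.973 (SD 0.8). At 2.3 it was 2.260 or 2.251. The direction is the same and the bias is small.

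**Does the rule raise the chance of wrongly concluding minimal activation?**

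The plan defines no criterion for minimal. Take 5 or fewer of 17 over the limit as an illustration, at p = 0.5. With no interim look the chance is 0.072. With the rule, and a dose change counted as non-support, it is 0.070. Looking only at trials that kept the dose, it is 0.070/0.656 = 0.107.

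**The case against.** Three stronger readings are tempting, and the documents support none of them.

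- *A reader might infer that the data go exactly when they contradict the hypothesis.* They do not. One to three of six over the limit, or an ACTH rise without that UFC level, also speaks against minimal activation and is kept. The chance of one to three of six is 0.81 at p = 0.3 and 0.64 at p = 0.5.
- *A reader might infer that the hypothesis cannot be fairly tested even if the dose is kept.* At p of 0.3 or less, the six are dropped in at most 7% of trials and the bias is about 1 point. At p = 0.7 the retained pooled share is still 0.61, which few would call minimal.
- *A reader might infer that the rule can only favour the hypothesis.* After a trigger, no 50 mg data remain to support it, and the dose change is itself visible evidence against it. Counted that way, the rule acts like a futility stop and does not raise the overall chance of a false conclusion (0.070 against 0.072).

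It is also fair to say that the binomial figures describe the interim trigger, whereas the planned HPA outcomes are continuous between-treatment changes. They show direction and rough scale only.

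What survives is the gap on the trigger branch. The futility-stop defence works only if a dose change is declared to count against the hypothesis, and the plan does not say so. Nor does it commit to reporting the HPA results that led to the change.

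**Conclusion.** The point holds in a limited form. Followed as written, a triggered dose change leaves the final analysis with no data at the regimen named in the secondary hypothesis, and nothing elsewhere in the plan repairs this. That conclusion rests on the wording alone and needs no assumption about p.

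The bias when the dose is kept is secondary and modest: about 1, 4 and 9 points at p = 0.3, 0.5 and 0.7 with 17 subjects, under the assumed binomial model for a quantity that is not an endpoint. The primary insulin-sensitivity analysis is not affected by this point.

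One limit on what can be gained: the plan gives no definition or margin for minimal activation and plans only two-sided difference tests, so keeping the data in does not by itself make the hypothesis confirmable.

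**What to change.** In the interim paragraph of STUDY ANALYSIS:

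1. Limit the exclusion of the first six to the insulin-sensitivity and other metabolic analyses at the new dose.
2. State that HPA outcomes for all subjects treated at 50 mg every 6 hours, including the first six, are analysed and reported for the secondary hypothesis whatever the interim result.
3. State that a triggered dose change is reported as not supporting that hypothesis.
4. State that HPA results at any other dose are reported separately.

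Optionally, if the dose is kept, show HPA results for subjects 7 onward as a sensitivity estimate. It is free of the interim screen but less precise, with 17 − 6 = 11 subjects.

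The cost is a few sentences. No new subjects or measurements are needed, and the dose and the interim trigger are left as they stand.
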